1.1.2.2.2. Abaloparatide-sMTS

To date, several different abaloparatide-sMTS formulations have been evaluated in a total of 4 Phase 1 studies and one Phase 2 study, including an abaloparatide-sMTS phosphate buffered saline (PBS) formulation (abaloparatide-sMTS PBS) and an optimized formulation (abaloparatide ZnCl₂·HCl).

The abaloparatide-sMTS PBS formulation has similar abaloparatide maximum concentration, but lower abaloparatide area under the concentration-time curve (AUC) than the reference abaloparatide-SC 80 µg treatment. This abaloparatide-sMTS formulation was evaluated in 3 completed Phase 1 studies in healthy postmenopausal women, Studies BA058-05-004, BA058-05-006, and BA058-05-008. These studies were conducted to evaluate the pharmacokinetics (PK), safety, and local tolerability of different doses of abaloparatide-sMTS and to evaluate the impact of the application site and the duration of application (wear time) on PK, safety, and local tolerability.

A Phase 2, dose-range-finding study, Study BA058-05-007, was also conducted with the abaloparatide-sMTS PBS formulation to evaluate the PK, efficacy, and safety of 3 doses of abaloparatide-sMTS (50, 100, and 150 μ g) compared to 80 μ g abaloparatide-SC and placebo-sMTS in postmenopausal women with osteoporosis. The results from this study with the abaloparatide-sMTS PBS formulation did not support the selection of this abaloparatide-sMTS formulation for further clinical development, although it did provide important insights into the exposure-response relationship between abaloparatide-sMTS and increases in BMD.

BA058-05-015 was a Phase 1 study to select an optimized formulation and dose for abaloparatide-sMTS to be used in the Phase 3 study. From the PK data in this clinical study, abaloparatide-sMTS Formulation W-1 (abaloparatide ZnCl₂·HCl) 300 µg applied to the thigh for 5 minutes was selected for further clinical development.

Full details of the results of clinical trials conducted with abaloparatide-SC and abaloparatide-sMTS are provided in the Investigator's Brochure.

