7.1.2. Serious Adverse Event

An SAE is any AE that results in any of the following:

- Death
- Life-threatening: The term "life-threatening" in the definition of "serious" refers to an event/reaction in which the subject was at risk of death at the time of the event/reaction; it does not refer to an event/reaction which hypothetically might have caused death if it were more severe
- Hospitalization or prolongation of existing hospitalization
- Persistent or significant disability/incapacity (ie, substantial disruption of the ability to conduct normal life function)
- Congenital anomaly/birth defect
- Important medical events that may not result in death, are life-threatening, or require hospitalization may be considered serious when, based upon appropriate medical judgment, they may jeopardize the subject and may require medical or surgical intervention to prevent 1 of the outcomes listed in this definition. Examples of such medical events include allergic bronchospasm requiring intensive treatment in an emergency room or at home, blood dyscrasias or convulsions that do not result in subject hospitalization, or the development of drug dependency or drug abuse

All AEs of osteosarcoma will be reported as SAEs.

All treatment-related AEs/SAEs must be followed until resolution (subject has returned to baseline status of health) or until stabilization (the Investigator does not expect any further improvement or worsening of the reported event), or until the subject is lost to follow-up.

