7.1.4. Recording an Adverse Event

All AEs/SAEs will be entered into the electronic database.

Planned hospital admissions or surgical procedures for an illness or disease that existed before the subject was enrolled in the study are not to be considered AEs unless they occur at a time other than the planned date or the pre-existing illness or disease worsens after enrollment into the study.

Fractures identified during the study are not to be recorded as AEs unless the subject is hospitalized, the fracture is complicated, or the Investigator considers the fracture to be unrelated to the subject's underlying osteoporosis. All fractures will be identified and evaluated as part of the disease assessment and will be documented in the eCRF and by collection of source documents.

For both serious and non-serious AEs, the Investigator must determine the intensity of the event and the relationship of the event to study drug administration (abaloparatide-SC and abaloparatide-sMTS). Intensity for each AE will be defined according to the following criteria:

Intensity Definition

Mild Awareness of sign or symptom, but easily tolerated

Moderate Discomfort enough to cause interference with normal daily

activities

Severe Inability to perform normal daily activities

If the intensity of an adverse event changes within a day, the maximum intensity should be recorded. If the intensity changes over a longer period of time, the changes should be recorded as separate events (having separate onset and stop dates for each intensity).

Relationship to study drug or device, defined as study drug administration, will be determined by the Investigator according to the following criteria:

Relationship Definition

None No relationship between the event and the administration of study drug. The event is related to other etiologies, such as concomitant

medications or subject's clinical state.

Unlikely The current state of knowledge indicates that a relationship to study

drug administration is unlikely or the temporal relationship is such that

study drug administration would not have had any reasonable

association with the observed event.

Possible A reaction that follows a plausible temporal sequence from

administration of the study drug and follows a known response pattern to the suspected study drug. The reaction might have been produced by the subject's clinical state or other modes of therapy administered to the

subject.

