Probable A reaction that follows a plausible temporal sequence from

administration of the study drug and follows a known response pattern

to the suspected study drug. The reaction cannot be reasonably

explained by the known characteristics of the subject's clinical state or

other modes of therapy administered to the subject.

For the purpose of safety analyses, all AEs that are classified with a relationship to study drug administration of possible or probable will be considered treatment-related events. The AE will be determined to be device-related if it is identified to have had a probable or possible causal relationship to the investigational device.

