7.1.4.1. Serious and Unanticipated Adverse Device Effects for Abaloparatide-sMTS

An adverse device effect is defined as any adverse event that may or may not be related to the investigational abaloparatide-sMTS device and should be reported as an AE (Section 7.1), and includes AEs resulting from insufficient or inadequate instructions for use, deployment, implantation, installation, operation, malfunction, use error or from intentional misuse of the investigational medical device.

An unanticipated adverse device effect (UADE) is defined as any serious adverse effect on health or safety or any life-threatening problem or death caused by, or associated with, the abaloparatide-sMTS device, if that effect, problem, or death was not previously identified in nature, severity, or degree of incidence in the Study Reference Manual, or any other unanticipated serious problem associated with a device that relates to the rights, safety, or welfare of subjects.

The Investigator and the Sponsor will immediately conduct an evaluation of any UADE occurring with abaloparatide-sMTS. The results of the evaluation will be reported to the IRB within 10 days of the Investigator and/or the Sponsor becoming aware of the event. If it is determined by the Investigator and the Sponsor to present an unreasonable risk to study subjects, all investigations or parts of the investigation presenting that risk will be terminated as soon as possible. Termination will occur not later than 5 working days after the Investigator and the Sponsor makes this determination and not later than 15 working days after first receiving notice of the event. The Investigator and the Sponsor will not resume an investigation terminated under these conditions without an additional IRB approval.

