7.1.9. Regulatory Agency, Institutional Review Board, Ethics Committee and Site Reporting

The Sponsor and/or the clinical contract research organization (CRO) are responsible for notifying the relevant regulatory authorities/US central IRBs/European Union central IECs of related, unexpected SAEs.

The Investigator is responsible for notifying the Sponsor, CRO, and local IRB, local IEC, or the relevant local regulatory authority of all SAEs that occur at his or her site as required.

Any SAEs that occur at any time after completion of the study, which are considered by the Investigator to be related to study treatment, must be reported to the Sponsor or its designee. The contact may be by phone or email.

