### **4.6.1. Adverse Events**

All AEs will be coded to SOC and PT using MedDRA Version 24.0.

Analyses of AEs will be performed for those events that are considered to be TEAEs. A TEAE is defined as any AE that was absent (i.e., had not occurred) or had resolved prior to the start of study drug, and which occurred on or after the date of the first dose of study drug and within 30 days of the last dose of study drug; or any AE that started prior to the first dose of study drug, was ongoing after study treatment started, and increased in severity after the start of study drug and within 30 days of the last dose of study drug. AEs with missing onset dates will be handled according to the Conventions for Imputing Missing Dates in [Appendix A](#).

TEAEs reported as unanticipated adverse device effects (UADE) or medical device reports (MDR) are those AEs with “Yes” to all of the following three questions on the AE eCRF: “Serious Event?”, “Was AE related to device?”, and “Would you consider this AE unexpected?”. For North American sites, unanticipated device-related SAEs will be reported as UADE for abaloparatide-sMTS, and will be reported as MDR for subjects on abaloparatide-SC. For European sites, unanticipated device-related SAEs will be reported as UADE for subjects on either abaloparatide-sMTS or abaloparatide-SC.

In any tabulation of TEAEs, a subject contributes only once to the count for a given PT and/or SOC, or for a time period category. For summaries by severity, a subject with multiple occurrences of a TEAE will be represented under the most severe occurrence. For summaries by relationship to study drug, a subject with multiple occurrences of a TEAE will be represented under the most related occurrence.

An overall summary of AEs will be presented by treatment group and overall, including the number and percentage of subjects reporting AEs, TEAEs, study treatment-related TEAEs (with probable or possible relationship to study drug), severe TEAEs, treatment-related severe TEAEs, serious TEAEs, treatment-related serious TEAEs, TEAEs leading to study drug interruption, TEAEs leading to study drug withdrawal, TEAEs leading to discontinuation from study, TEAEs related to the device, and TEAEs resulting in death.

The following summaries will be presented:

- TEAEs by SOC and PT
- TEAEs by SOC, PT, and region (North America, Europe)
- TEAEs by SOC, PT and Maximum Severity (mild, moderate, or severe)

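### Both causality grades that count as related require a known response pattern, so an event new in nature cannot be graded treatment- or device-related in either arm

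*Protocol*

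**What the plan says.** Protocol Section 7.1.4 gives investigators a four-grade scale for relationship to study drug or device.

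- **None**: there is no relationship, and the event is due to something else.
- **Unlikely**: current knowledge speaks against a link, or the timing does not fit.
- **Possible**: plausible timing from "administration of the study drug and follows a known response pattern to the suspected study drug", with another explanation available.
- **Probable**: the same timing and pattern requirement ("administration of the study drug and follows a known response pattern"), with no other reasonable explanation.

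The section then states that "all AEs that are classified with a relationship to study drug administration of possible or probable will be considered treatment-related events". It makes an event device-related on the same two grades. SAP Section 4.6.1 uses the same rule for "study treatment-related TEAEs (with probable or possible relationship to study drug") and does not redefine the grades.

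Other rules depend on the grade:

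- Protocol 7.1.2: "All treatment-related AEs/SAEs must be followed until resolution" or stabilization. Section 7.1.7 repeats this for AEs.
- Protocol 7.1.5: SAEs arising after study completion are reportable if the investigator considers them related.
- Protocol 7.1.9: regulators and central committees are notified, down to "European Union central IECs of related, unexpected SAEs".
- Protocol 7.1.4.1: a UADE is a serious device effect that "was not previously identified in nature, severity, or degree of incidence in the Study Reference Manual".
- SAP 4.6.1: a UADE or MDR is counted only if the serious, device-related and unexpected questions on the eCRF are all answered yes.

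**The concern.** A causality scale should let an investigator record a suspected link whether or not that kind of reaction has been seen before. Here the known pattern is a required condition of both related grades. Elsewhere the plan depends on identifying events that are related and also new, and the scale does not allow that combination when the novelty lies in the nature of the event.

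At stake are the outputs and actions that use the grade: the treatment-related, related-severe, related-serious and device-related TEAE summaries, the UADE/MDR listing, follow-up of treatment-related events, reporting of related SAEs after study completion, and regulatory notification. The primary efficacy analysis is not involved.

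**Working it through.** No arithmetic applies. The check reads the four definitions in Protocol 7.1.4 as a decision rule and applies them to one test event: plausible timing, no other cause, and a kind of reaction not previously known for the study drug.

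| Grade | Condition | Does the test event meet it? |
|---|---|---|
| None | No relationship; due to another etiology | No: there is no other etiology |
| Unlikely | Knowledge against a link, or implausible timing | No: timing fits, and absence of knowledge is not knowledge against |
| Possible | Plausible timing and known pattern | No: the pattern is not known |
| Probable | Plausible timing and known pattern, no other explanation | No: the pattern is not known |

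The event has no valid grade, and neither related grade is open to it. By contrast, an event with plausible timing and a known pattern is Possible if another cause could explain it and Probable if not.

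**Is there another route to a related grade?** The device question gives none. Section 7.1.4 applies the same scale to drug and device, and device-related also means possible or probable. The SAP refers to a yes/no eCRF item on device relatedness, but neither document gives separate criteria for answering it. No other clause in either document lets a new reaction be graded related.

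**Which later rules conflict?**

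1. The UADE definition in 7.1.4.1 covers effects not previously identified in nature, severity or incidence. The SAP derivation requires a yes on device-related. An event new in nature cannot get that yes under 7.1.4, so the new-in-nature part of the category is empty if the definitions are followed.
2. Section 7.1.9 requires related and unexpected together. The same part is empty there.
3. An event of a known kind that is unexpected only in severity or incidence still has a known pattern. It can be graded related, so this part of both categories works as intended.

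**What does not depend on the grade?**

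- All-causality, severe, serious, interruption and withdrawal TEAE tables (SAP 4.6.1).
- Identification and all-causality counts of AESIs (SAP 4.6.2). The treatment-related and device-related rows of the AESI overview do inherit the grade.
- Local tolerance scores (SAP 4.6.4), and the reporting of every application-site skin reaction as an AE (Protocol 7.1.1).
- Reporting of every SAE within 24 hours up to 30 days after the last dose (Protocol 7.1.5).

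**The case against.** The strongest case on the other side has four parts.

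**The gap is narrow.** Known pattern is not defined. Both arms receive the same active ingredient, so reactions known from the injection are a known pattern for the patch too. Protocol 1.1.2.2.2 reports patch formulations studied in four Phase 1 studies and one Phase 2 study. The protocol also lists 12 local signs, 5 symptoms and 3 skin AESIs in advance, so typical patch reactions are anticipated. This stands. It limits how often the gap will matter, but it does not open a grade for an event that really is new.

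**Other safeguards catch the important events.** Besides the routes that do not depend on the grade, severe site reactions, and those ongoing at Month 12, are followed until resolved or stabilized (6.6.3.1). Skin AESIs are photographed until they resolve (7.1.3.1). The UADE definition itself speaks of effects caused by or associated with the device, which is wider than the four-grade scale. This stands for local skin reactions and in-study SAE capture. It does not help a new systemic reaction in the related tables or in related-and-unexpected notification, and the SAP's UADE/MDR rule still runs through the device-related answer.

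**Investigators will use judgement.** Probably so, but that means departing from the written definitions, with no assurance that about 125 sites would do so in the same way.

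**Changing the scale mid-trial has a price.** The SAP approvals are dated September 2021 and parts of the SAP describe conduct in the past tense. Events graded under two definitions would be hard to summarise. This stands and shapes the fix.

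A reader might go further and infer a bias in favour of the patch. The injection is marketed and had 824 women randomized to it in its pivotal study, whereas on the patch side "BA058-05-015 was a Phase 1 study to select an optimized formulation and dose for abaloparatide-sMTS to be used in the Phase 3 study". The documents do not support that inference. The wording is identical in both arms, a new reaction to the injection is barred as well, and nothing gives the frequency of novel reactions in either arm. A subject with even one known related reaction stays in the overall related-TEAE count, and the safety summaries are mainly descriptive.

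**Conclusion.** The point holds as a defect in the definitions. Under Section 7.1.4 as written, no event that is new in nature can be graded treatment-related or device-related in either arm, and an event with plausible timing and no other cause has no valid grade at all. This contradicts the plan's own reliance on related events that are new in nature. Events unexpected only in severity or incidence are not affected.

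Within its scope the exclusion is complete. The number of events concerned cannot be estimated from the documents. The gap may matter more for the newer patch formulation, but neither the size nor the direction of any effect on the arm comparison is shown.

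The conclusion rests on two readings: that both elements of the Possible and Probable definitions are required, as the conjunction says, and that known pattern means a kind of reaction already recognised for the study drug. It deserves correction because the repair is cheap and the affected events are informative for a new product.

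**What to change.** In Protocol 7.1.4 and the eCRF completion guidance:

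1. Define Possible as plausible timing in relation to study drug or device administration where a causal relationship cannot be excluded, whether or not the event follows a known pattern.
2. For Probable, make a known pattern supporting evidence, not a condition.
3. Apply the same text to the device-relatedness item in both arms, so that the SAP's UADE/MDR rule can capture events new in nature.

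If grading is already under way, keep the grades as recorded. Add to SAP 4.6.1 a supplementary related-TEAE summary that also counts events graded None or Unlikely with plausible timing and no documented alternative cause. Fix the selection rule before database lock, while aggregated data by arm are still withheld under SAP 1.2.3.

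The cost is a paragraph of protocol text with matching guidance, or one extra table and a limited review of events. The downside is that somewhat more AEs will be graded related.

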7.1.4.1. Serious and Unanticipated Adverse Device Effects for Abaloparatide-sMTS

An adverse device effect is defined as any adverse event that may or may not be related to the investigational abaloparatide-sMTS device and should be reported as an AE (Section 7.1), and includes AEs resulting from insufficient or inadequate instructions for use, deployment, implantation, installation, operation, malfunction, use error or from intentional misuse of the investigational medical device.

An unanticipated adverse device effect (UADE) is defined as any serious adverse effect on health or safety or any life-threatening problem or death caused by, or associated with, the abaloparatide-sMTS device, if that effect, problem, or death was not previously identified in nature, severity, or degree of incidence in the Study Reference Manual, or any other unanticipated serious problem associated with a device that relates to the rights, safety, or welfare of subjects.

The Investigator and the Sponsor will immediately conduct an evaluation of any UADE occurring with abaloparatide-sMTS. The results of the evaluation will be reported to the IRB within 10 days of the Investigator and/or the Sponsor becoming aware of the event. If it is determined by the Investigator and the Sponsor to present an unreasonable risk to study subjects, all investigations or parts of the investigation presenting that risk will be terminated as soon as possible. Termination will occur not later than 5 working days after the Investigator and the Sponsor makes this determination and not later than 15 working days after first receiving notice of the event. The Investigator and the Sponsor will not resume an investigation terminated under these conditions without an additional IRB approval.

7.1.4.2. Medical Device Reporting for Abaloparatide-SC

Sites will report medical device reports (MDRs) that reasonably suggest that abaloparatide-SC may have caused or contributed to a death or serious injury or has malfunctioned and the malfunction of the device would be likely to cause or contribute to a death or serious injury if the malfunction were to recur, including events occurring as a result of device failure, malfunction, improper or inadequate design, manufacture, labeling, or user error.

A serious injury is an injury or illness that:

- Is life threatening
- Results in permanent impairment of a body function or permanent damage to a body structure
- Necessitates medical or surgical intervention to preclude permanent impairment of a body function or permanent damage to a body structure

If the Investigator learns of any MDR after a subject has been discharged from the study, and such incident is reasonably related to abaloparatide-SC, the Investigator will promptly notify RADIUS.

